### 9.2.1 Use of screening results from another HVTN study

If a participant screens for an HVTN study at the same HVTN CRS but then does not join that study, screening results from that effort may be applied to the screening for this protocol, as long as the screening was done under participant consent, the participant has signed a consent form to begin screening for this study, and the tests were conducted within the time periods specified in the eligibility criteria (see Sections 7.1 and 7.2).

### 9.3 Enrollment visit

Enrollment is simultaneous with baseline biopsy collection on day –14. At the baseline biopsy visit, cervical, vaginal, and/or rectal biopsies and mucosal secretion specimens will be collected. These samples will serve as baseline controls and will help to assess both the participants' acceptability of the biopsy procedures and their fitness to continue with mucosal biopsy collections. Participants with conditions not amenable to biopsy sampling, not willing to continue in the trial after these baseline biopsies have been performed, or not able to provide mucosal secretions, will not be randomized. Participants not willing to continue in the trial after these baseline biopsies have been performed may be replaced.

Randomization will occur after the mucosal collection. The HVTN CRS requests the randomization assignment via a Web-based randomization system. In general, the time interval between randomization and infusion should not exceed 4 working days. However, circumstances may require a participant's infusion visit to be changed. This may exceed the 4-day randomization time limit. At the enrollment biopsy collection visit, the following procedures are performed:

- Abbreviated physical examination, including weight, vital signs, and a symptom-directed evaluation by history and/or appropriate physical exam based on participant self-reported symptoms or complaints;
- Assessment of concomitant medications the volunteer is taking, including prescription and nonprescription drugs, vitamins, topical products, alternative/complementary medicines (eg, herbal and health food supplements), recreational drugs, vaccinations, and allergy shots (see Section 9.2);
- Assessment of any new or unresolved Unsolicited AEs/intercurrent illnesses;
- Urine or serum pregnancy test (for participants who were assigned female sex at birth);
- Risk reduction counseling (see Section 9.7)
- For participants capable of becoming pregnant, pregnancy prevention assessment (see Sections 9.2 and 9.7)
- Social impact assessment
- Specimen collection (including mucosal and biopsy samples as described in Section 9.6);
- Laboratory tests (see Appendix E), including:

- Blood hormone panel (estradiol and progesterone [assigned female sex at birth only])
- Confirm that participants received HIV test results from previous visit. If not, provide test results and post-test counseling as appropriate.

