### **5.3 Exploratory objectives**

*Exploratory objective 1:*

To assess the acceptability and tolerability of repeat mucosal sampling, including secretions and biopsies, for application in future studies

*Exploratory objective 2:*

To develop predictive mucosal population pharmacokinetic models of VRC07-523LS administered IV

*Exploratory objective 3:*

To conduct analyses related to furthering the understanding of HIV, monoclonal antibodies, immunology, vaccines, and clinical trial conduct

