## 6 Statistical considerations

### 6.1 Accrual and sample size calculations

Recruitment will target accruing a total of 24 healthy, HIV-1–uninfected adult participants in two treatment groups, with 12 participants assigned to each group.

In Group 1, all study participants will receive three IV administrations of VRC07-523LS at the 10 mg/kg dose level. In Group 2, all study participants will receive three IV administrations of VRC07-523LS at the 30 mg/kg dose level.

In both groups, the three infusions will be administered every 16 weeks.

Participants will be randomly assigned to either one of the groups. Groups 1 and 2 will open to randomization at the same time.

In Groups 1 and 2, every study participant will be followed for 12 months (including 8 months of product administration plus 4 months of follow-up) from the day of first product administration.

To ensure balance in the trial of both sexes assigned at birth, the trial will enroll at least and approximately 50% of participants assigned female sex at birth. Randomization will be stratified by assigned sex at birth to ensure balance within each treatment group.

The times at which samples will be collected are listed in [Table 9-1](#) and [Table 9-2](#) for each mucosal site and the blood.

Since enrollment is concurrent with the first biopsy sample collection, all participants will provide some data regarding tolerability of mucosal sample collections. For analyses of VRC07-523LS levels in serum and mucosa and of data from ADA assays, it is possible that data may be missing for various reasons, such as participants terminating from the study early, problems in shipping specimens, or high assay background. Immunogenicity data from 17 phase 1 and 2 phase 2a HVTN vaccine trials, which began enrolling after June 2005 (data as of September 2014), indicate that 17% is a reasonable estimate for the rate of missing data. In HVTN 104 (phase 1 trial of VRC01), approximately 10-15% of drug concentration data were missing at the primary timepoints.

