#### 6.4.3.5 Acceptability of study product or procedure

Acceptability of study product administration and infusion procedures will be tabulated by reason and treatment arm.

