## Appendix F Procedures at HVTN CRS

Procedure	01 	02	03	04	05	06	07	08	09	10
	Day:	D -14	D0	D14	D112	D126	D224	D238	D336	D350
	Week:	W -2	W0	W2	W16	W18	W32	W34	W48	W50
Procedure	Scr	Enr	Inf 1		Inf 2		Inf 3			
Study procedures										
Signed screening consent (if used)	X	—	—	—	—	—	—	—	—	—
Assessment of understanding	X	—	—	—	—	—	—	—	—	—
Signed protocol consent	X	—	—	—	—	—	—	—	—	—
Medical history	X	—	—	—	—	—	—	—	—	—
Complete physical exam	X	—	—	—	—	—	—	—	X	—
Confirm eligibility and obtain demographics	X	—	—	—	—	—	—	—	—	—
Randomize	—	X	—	—	—	—	—	—	—	—
Abbreviated physical exam	—	X	X	X	X	X	X	X	—	—
Risk reduction counseling 	X	X	X	X	X	X	X	X	X	X
Pregnancy prevention assessment 	X	X	X	X	X	X	X	X	X	X
Behavioral risk assessment questionnaire 	X	—	—	—	X	—	X	—	X	—
Social impact assessment	—	X	X	X	X	X	X	X	X	X
Social impact assessment questionnaire	—	—	—	—	X	—	X	—	X	—
Mucosal sampling acceptability questionnaire	—	—	X	—	—	X	—	—	X	—
Concomitant medications	X	X	X	X	X	X	X	X	X	X
Intercurrent illness/Unsolicited AEs	—	X	X	X	X	X	X	X	X	X
AESI	—	—	—	X	—	X	—	X	—	—
HIV infection assessment 	X	—	—	—	X	—	X	—	X	—
Confirm HIV test results provided to participant 	—	X	—	—	—	X	—	X	—	X
Safety contact 	—	—	—	—	—	—	—	—	—	X
Study product administration										
Infusion 	—	—	X	—	X	—	X	—	—	—
Solicited AE assessment 	—	—	X	—	X	—	X	—	—	—
Local lab assessments										
Screening HIV test	X	—	—	—	—	—	—	—	—	—
Hepatitis B, Hepatitis C	X	—	—	—	—	—	—	—	—	—
Syphilis	X	—	—	—	—	—	—	—	—	—
Hormone panel	—	X	—	X	X	X	X	X	X	X
Pap smear 	X	—	—	—	—	—	—	—	—	—
Safety labs										
CBC, differential	X	—	—	X	—	X	—	X	—	—
Chemistry panel 	X	—	—	X	—	X	—	X	—	—
Urine collection										
Urine dipstick 	X	—	—	X	—	X	—	X	—	—
Pregnancy (urine or serum HCG) 	X	X	X	X	X	X	X	X	X	X
Chlamydia/Gonorrhea 	X	—	—	X	—	—	—	X	X	—
Rectal swab collection										
Chlamydia/Gonorrhea 	X	—	—	X	—	—	—	X	X	—
Cervical/vaginal swab collection										
Chlamydia/Gonorrhea 	X	—	—	X	—	—	—	X	X	—
Trichomonas vaginalis 	X	—	—	—	—	—	—	—	—	—
Bacterial vaginosis 	X	—	—	X	—	—	—	X	X	—
Yeast 	—	—	—	—	—	—	—	—	—	—
Mucosal biopsy collection										
Colorectal biopsy	—	X	—	X	—	—	—	X	X	—

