4 COHORT DEFINITION

Participants will enroll in the study at the first biopsy collection. Only participants who remain in the trial after completion of the first biopsy visit will be randomized. Since enrollment is concurrent with the first biopsy sample collection, all enrolled participants will provide some data regarding the tolerability of mucosal sample collections, regardless of if they are randomized.

Since randomization followed with receiving the first study product administration, all randomized participants will provide some data regarding the safety of the study product. Participants who are randomized but do not receive the study product are released from randomization, so the randomized cohort will consist only of participants who received study product and contribute some data regarding the safety of the study product.

All safety data from randomized participants will be analyzed according to the initial randomization assignment regardless of how many infusions they received. The analysis is a modified intent-to-treat analysis in that individuals who are enrolled but not randomized do not contribute immunogenicity data about the study product and hence are excluded.

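### The mucosal-sampling acceptability questionnaire is first scheduled after the baseline-biopsy gate, and no planned table covers its results or the participants who leave at that gate

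*Protocol*

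**What the plan says.** Protocol 5.3 sets exploratory objective 1: "To assess the acceptability and tolerability of repeat mucosal sampling, including secretions and biopsies, for application in future studies".

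**The gate.** Protocol 9.3 makes enrollment simultaneous with the D-14 biopsy and says that the baseline samples "will help to assess both the participants' acceptability of the biopsy procedures and their fitness to continue with mucosal biopsy collections". Participants with a condition not amenable to biopsy are not randomised, nor are those "not willing to continue in the trial after these baseline biopsies have been performed, or not able to provide mucosal secretions, will not be randomized". On replacement: "Participants not willing to continue in the trial after these baseline biopsies have been performed may be replaced". Under Protocol 6.2, accrual runs until 24 people have had a first infusion. SAP 4 adds that anyone randomised but not given product is released from randomisation.

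**The instrument.** The Appendix F row "Mucosal sampling acceptability questionnaire" is marked at visits 3 (D0), 6 (W18) and 9 (W48). It is blank at visit 2 (D-14), and the visit 2 procedure list in 9.3 omits it. Section 9.12 includes it among assessments that sites should consider at early termination.

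**The analysis.** Protocol 6.4.3.5 reads in full: "Acceptability of study product administration and infusion procedures will be tabulated by reason and treatment arm". Appendix F has no questionnaire on infusion acceptability.

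**Who contributes.** Protocol 6.1 says that, because enrollment coincides with the first biopsy, "all participants will provide some data regarding tolerability of mucosal sample collections". SAP 4 says the same and extends it to those not randomised.

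**The concern.** Section 9.3 treats the baseline visit as a test of whether participants accept the procedures, but the instrument that records acceptance is not scheduled there. A participant who decides after one round of biopsies not to go on leaves before the first scheduled questionnaire. That is the clearest kind of non-acceptance, and if the place is refilled it drops out of the questionnaire's denominator.

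Objective 1 is meant to inform future studies. A planner needs to know how many people stop after a first biopsy and why. If those people are not asked and have no column in any table, the questionnaire result describes people who have already accepted one round, and any resulting error favours acceptability.

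The analysis text has a second gap, which matters even if nobody leaves early: the one acceptability table planned is about infusion, and the questionnaire that is collected has no stated analysis.

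**Working it through.** The documents state no figure, target or assumed refusal rate for objective 1, so there is nothing to reproduce. The check is mainly a comparison of provisions.

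**Step 1. Order of events (9.3, 6.2, Appendix F).**

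| Event | Visit |
|---|---|
| Enrollment, baseline biopsies and secretions | 2 (D-14) |
| Decision to continue; randomisation | 2, after collection |
| First scheduled acceptability questionnaire | 3 (D0) |
| Later questionnaires | 6 (W18), 9 (W48) |

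Two groups can miss visit 3: those not randomised, and those who withdraw between randomisation and D0. For both, the only route to the questionnaire is the discretionary one in 9.12.

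**Step 2. Where early leavers could be reported.** Early termination (6.4.3.4), solicited and unsolicited adverse events (6.4.3.1, 6.4.3.2) and acceptability (6.4.3.5) are all tabulated by treatment arm. A non-randomised participant has no arm. The SAP lists no mucosal-sampling acceptability table.

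**Step 3. What is collected from everyone enrolled.** Unsolicited adverse events are reported from enrollment (11.2.2), and visit 2 includes adverse-event and social-impact assessments (9.3, Appendix F). Tolerability data therefore exist for all enrolled. The collection gap is confined to questionnaire-based acceptability.

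**Step 4. Illustration of size.** Let k be the number who leave before first infusion because of the sampling and are replaced. The documents do not give k; it is an assumption here. With 24 infused, and ignoring departures for other reasons, acceptance of the first round over all enrolled is 24/(24 + k). The interval is the 95% score interval that the protocol uses. As a check on the method, the score upper bound for zero events is z²/(n + z²) with z² = 3.84, which gives 24.2% for 0/12 and 13.8% for 0/24, matching Protocol Table 6-2.

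| k (assumed) | All enrolled | Acceptance | 95% score interval |
|---|---|---|---|
| 0 | 24/24 | 100% | 86.2 to 100 |
| 1 | 24/25 | 96.0% | 80.5 to 99.3 |
| 2 | 24/26 | 92.3% | 75.9 to 97.9 |
| 4 | 24/28 | 85.7% | 68.5 to 94.3 |

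Among the 24 infused, first-round acceptance is 100% by construction in every row.

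**Step 5. Nearest evidence on k.** Protocol 4.8 reports that HVTN 116, with 79 enrolled, had no terminations due to discomfort with the procedures. The score upper bound for 0/79 is 3.84/(79 + 3.84) = 4.6%, equivalent to 24 × 0.046/0.954 ≈ 1.2 leavers per 24 infused. That is a different trial, and it did not measure willingness after a first biopsy, so this is context and not an estimate. It does suggest that k may be small, and the rows above k = 1 have no support in the documents.

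**The case against.** The case on the other side is substantial, and most of it stands.

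- Objective 1 covers tolerability as well as acceptability, and concerns repeat sampling. A reader might infer that the whole objective is answered only in people who already accepted the procedures. The documents do not support that: tolerability and adverse-event data come from everyone enrolled, and after the first infusion a participant may decline any collection (9.6) or stop biopsies (7.3.6) and stay in the trial, so later refusals remain visible.
- A reader might take the SAP 4 statement that "individuals who are enrolled but not randomized do not contribute immunogenicity data about the study product and hence are excluded" as removing these people from objective 1. It defines the modified intent-to-treat set for data about the product. The same section keeps the non-randomised as contributors on sampling tolerability.
- Not everyone stopped at the gate is a refuser. An unsuitable condition and inability to give secretions are not refusal, and unwillingness to continue in the trial can have causes other than the biopsy. Replacement is permitted, not automatic, and is stated for the unwilling only.
- Early leavers leave some trace. Refusing further participation is a listed termination reason (7.3.4), 6.4.3.4 tabulates terminations by reason, and sites keep screening and enrollment logs (2.3).
- The SAP describes itself as a pharmacokinetics plan to be updated before the final safety analysis (SAP 1), so its silence is partly a matter of scope.
- The gate itself is a reasonable choice, since it protects the mucosal endpoints.

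What remains is narrow. The questionnaire is unscheduled at the visit where first-round refusal occurs, its use at early termination is optional, the by-arm tables have no place for the non-randomised, and 6.4.3.5 names the wrong procedure for this objective.

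**Conclusion.** The point holds in limited form. Followed as written, the plan yields questionnaire-based acceptability data that can omit participants who leave between the baseline biopsy and first infusion, and it specifies no analysis of those data. If anyone leaves because of the sampling and is not asked, the direction is favourable to acceptability.

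The size cannot be stated. It depends on the number of such leavers and on how often sites use the optional questionnaire, and the documents give neither. With no such leavers there is no bias. It would be tempting to quote a definite loss of acceptance, but the percentages in the illustration rest wholly on an assumed k.

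The consequence is confined to one part of an exploratory objective that has no hypothesis or target. The primary safety and drug-level objectives are unaffected. The change is worth making because it is cheap and because answers from people who have left cannot reliably be obtained later.

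**What to change.** 1. **Protocol 9.3 and Appendix F:** give the existing mucosal-sampling acceptability questionnaire at visit 2, after collection and before randomisation. Alternatively, make it required in 9.12 for anyone enrolled but not infused.
2. **Protocol 6.4.3.5 and the planned SAP update:** name mucosal-sampling acceptability and tabulate it over all enrolled participants, by arm, with a separate column for the non-randomised.
3. **Same table or a companion:** report separately the numbers and reasons for non-randomisation, replacement and later refusal of a collection. Count as non-acceptance only withdrawals or refusals attributed to the sampling. Keep medical contraindication, inability to give secretions and unrelated reasons apart, since counting them as refusals would bias the result the other way.

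The cost is one more short questionnaire at a visit that already takes place, one table, and wording changes in the protocol and SAP. The reported acceptability may be less favourable.

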#### 9.4 Infusion visits

At all infusion visits, the following procedures are performed before study product administration:

- Abbreviated physical examination, including weight, vital signs, and a symptom-directed evaluation by history and/or appropriate physical exam based on participant self-reported symptoms or complaints;
- Assessment of any new or unresolved Unsolicited AEs/intercurrent illnesses (as described in Section 11.2.2);
- Assessment of concomitant medications (Section 9.2);
- Urine or serum pregnancy test (for participants who were assigned female sex at birth).
- Blood collection (see Appendix E)
- Mucosal secretion collection at infusions 2 and 3 only (see Section 9.6 and Appendix E).

Following completion of all procedures in the preceding list, and if results indicate that infusion may proceed, infusion is administered (see Sections 8.4 and 8.5).

Administration of all infusions during an infusion visit must be accomplished within 1 calendar day.

Immediately following infusion, the participant remains in the clinic for observation. See the HVTN 128 SSP for details regarding infusion visit protocols and subsequent infusion observation and Solicited AE assessment procedures (Section 9.10) that HVTN CRSs must follow. The HVTN CRS will make arrangements to be in contact with the participant during the Solicited AE period (as described in Section 9.10 and the HVTN 128 SSP).

The following procedures may be performed prior to, during, or following first infusion (see Appendix E and Appendix F):

- HIV infection assessment;

- Risk reduction counseling (see Section 9.7);
- For participants capable of becoming pregnant, pregnancy prevention assessment (see Sections 9.2 and 9.7);
- Administration of behavioral risk assessment questionnaire;
- Mucosal sampling acceptability questionnaire
- Assessment of new or unresolved social impacts (site staff will ask participant about the status of any unresolved social impacts and if s/he has experienced any new social impacts as a result of the trial participation);
- Administration of the social impact assessment questionnaire (types of impacts assessed involved personal relationships, health insurance, life insurance, educational or employment opportunities, housing, immigration, or travel);

For management of mAb reactions see the HVTN 128 SSP. The following procedures should be performed after a mAb reaction:

- mAb reaction clinical assessment
- mAb reaction blood collection.

## 9.5 Follow-up visits

Procedures will be performed at scheduled follow-up visits as specified in [Appendix D](#) and [Appendix F](#):

- Abbreviated physical examination including weight, vital signs, and a symptom-directed evaluation by history and/or appropriate physical exam based on participant self-reported symptoms or complaints; or
- Complete physical examination (performed at last scheduled clinic visit), including height, weight, vital signs, and clinical assessments of head, ears, eyes, nose, and throat; neck; lymph nodes; heart; chest; abdomen; extremities; neurological function; skin; and pelvic and/or rectal exam ;
- Risk reduction counseling (as described in Section 9.7);
- Pregnancy prevention assessment (as described in Section 9.2 and 9.8);
- Assessment of new or unresolved social impacts (site staff will ask participant about the status of any unresolved social impacts and if the participant has experienced any new social impacts as a result of trial participation);

- Administration of the social impact assessment questionnaire (types of impacts assessed involve personal relationships, health insurance, life insurance, educational or employment opportunities, housing, immigration, or travel);
- Assessment of new or continuing concomitant medications (as described in Section 9.2);
- Assessment of new or unresolved AEs/intercurrent illnesses or AESIs (as described in Section 11.2.2 and Appendix H);
- Mucosal sampling acceptability questionnaire
- Behavioral risk assessment questionnaire
- HIV diagnostic testing (see Section 9.7); A subsequent follow-up contact is conducted to provide post-test counseling and to report results to participant.
- Confirm that participants received HIV test results from previous visit. If not, provide test results and post-test counseling as appropriate;
- Specimen collection (including mucosal sampling as described in Section 9.6);
- Clinical laboratory tests, including:
  - CBC with differential,
  - Chemistry panel (see Section 9.2),
  - Blood hormone levels (estradiol and progesterone) for participants assigned female sex at birth only
  - Urine dipstick (urinalysis if appropriate; see Section 9.9),
  - Chlamydia/gonorrhea (for all participants)
  - Trichomonas vaginalis (for participants providing cervicovaginal samples when clinically indicated)
  - Bacterial vaginosis (for participants providing cervicovaginal samples, at indicated visits and when clinically indicated. See Appendix E)
  - Yeast (for participants providing cervicovaginal samples, when clinically indicated)
- Urine or serum pregnancy test (for participants who were assigned female sex at birth). Pregnancy test result required prior to biopsy collection.

CRS staff will contact study participants for a safety contact at Week 50 (see Appendix E and Appendix F).

